- ii. All adverse events will be reported to the safety officer monthly, and documented by standard IRB procedures and will be reported during the annual protocol review. Adverse events will be any event that does not satisfy the criteria for serious adverse events.
- iii. All serious adverse events will be reported immediately to the safety officer, IRB Research Subjects Advocate, and the NIH, in a timely manner (e.g. within 48 h) using the IRB Serious Adverse Report Event (SAE) form. The PI will sign each SAE, and a copy of the consent form signed by the subject will be included, with relevant sections highlighted. Serious adverse events are defined as:
 - 1. Death
 - 2. Life threatening injuries
 - 3. Inpatient hospitalization
 - 4. Persistent or significant disability/incapacity
 - 5. Congenital anomaly/birth defect.

For all serious adverse events that are determined by IRB to be definitely, probably, or possibly related to the study or interventions, the IRB will take whatever action(s) it deems appropriate, including but not limited to:

- 1. Modification of the protocol
- 2. Modification of the consent form document
- 3. Modification to the timetable for continuing review requirements
- 4. Suspension of new enrollment into the study
- 5. Suspension or termination of the study - If the study is suspended or terminated, it will be promptly reported to the NIH institute that has provided funding for the study. All other events not requiring suspension or termination shall be reported during the annual progress report.

ClinicalTrials.gov Requirements

This study will be registered on ClinicalTrials.gov. All relevant findings will be reported at the end of the study.

PROVISIONS TO PROTECT THE PRIVACY INTERESTS OF PARTICIPANTS

Every possible precaution will be taken to protect the privacy interests of subjects. Participation in this study is completely voluntary. Trained research personnel will explain the purpose of the study and intended use of subject's personal health information and precautions taken to keep the study information and data confidential.

Subjects have the right to refuse to answer to any questions they feel uncomfortable answering and the research team will mark these questions as unanswered. Furthermore, participants can refuse other objective tests in the protocol however if the participants refuse the majority of tests which affect the overall implementation of the study, the participants may be withdrawn from the study at the discretion of the principal investigator.

COMPENSATION FOR RESEARCH-RELATED INJURY

If the participant has any injury or illness from the study device or the procedures required for this study, the reasonable medical expenses required to treat such injury or illness may be paid for by the study sponsor.

STU#:00215607

The coverage for such injury or illness is only available if the Northwestern University principal investigator and study sponsor have decided that the injury/illness is directly related to the study device or procedures and is not the results of a pre-existing condition or the normal progression of the participant's disease, or because they have not followed the directions of the study doctor. If the participant's insurance is billed, they may be required to pay deductibles and copayments that apply. The participant should check with their insurance company about any such payments.

ECONOMIC BURDEN TO PARTICIPANTS

Costs associated with participation in the study will be offset by payment for each in person session (\$50 each training session and \$50 for each assessment).

CONSENT PROCESS

It is expected that the IRB will have the proper representation and function in accordance with federally mandated regulations. The IRB should approve the consent form and protocol. In obtaining and documenting informed consent, the investigator should comply with the applicable regulatory requirement(s), and should adhere to Good Clinical Practice (GCP) and to ethical principles that have their origin in the Declaration of Helsinki.

Before recruitment and enrollment onto this study, the patient will be given a full explanation of the study and will be given the opportunity to review the consent form. Each consent form must include all the relevant elements currently required by the FDA Regulations and local or state regulations. Once this essential information has been provided to the patient and the investigator is assured that the patient understands the implications of participating in the study, the patient will be asked to give consent to participate in the study by signing an IRB approved consent form.

Should there be amendment made to the consent form after the initial signature of the original, the subject will be required to sign a new consent form at their next visit. A researcher will review the changes and discuss the implications of the change.

Prior to a patient's participation in the trial, the written informed consent form must be signed and personally dated by the patient and by the person who conducted the informed consent discussion. The consent process will take place at the Shirley Ryan AbilityLab in Room 11-1402. Trained research personnel will guide the subject through consenting process. Subject will be given detailed explanation of the purpose, time line, commitment, procedures, data handling and privacy and confidentiality of information pertaining to the study.

NON-ENGLISH SPEAKING PARTICIPANTS

An interpreter who speaks the participant's primary language will be scheduled through the Shirley Ryan Ability Lab Interpreter Services department to attend all research appointments during which the participant is scheduled if necessary as determined by the participant.

PARTICIPANTS WHO ARE NOT YET ADULTS (infants, children, teenagers)

Participants will be asked their age upon study screen. Any child under the age of 18 years will be considered a minor. If the participant is determined a minor, every effort will be made to ensure the screening process proceeds with a parent or an authorized legal guardian present. The consent and protocol will be explained by a trained researcher to both the present parent/authorized legal guardian and the minor. The parent or authorized legal guardian will then be asked to consent on behalf of the minor, in accordance with the DHHS and the

STU#:00215607

USFDA's subpart D. The parent or authorized legal guardian will also be given the opportunity present at all training and testing sessions.

Consent will be obtained from one parent even if the other parent is alive, known, competent, reasonably available, and shares legal responsibility for the care and custody of the child. This will be done to ensure the protocol is carried through in a timely manner.

Permission will also be obtained from an authorized legal guardian if necessary. Efforts will be made to determine whether the guardian is in fact legally authorized by ensuring the child lives with the aforementioned guardian.

Assent will be obtained from all children. Verbal assent will be obtained for children unable to give written consent. Assent will be documented in the IRB approved consent form.

PROTECTED HEALTH INFORMATION (PHI AND HIPAA)

Subjects records will be kept completely confidential: Every possible precaution will be taken to protect the privacy interests of subjects. Participation in this study is completely voluntary. Trained research personnel will explain the purpose of the study and intended use of a subject's medical information and the precautions taken to keep the study information and data confidential. Data will be collected and kept confidential and compliant with HIPAA standards.

Participants will be assigned an alphabetical or numerical study ID. Identifying data will be kept in locked cabinets and password protected servers completely separate from de-identified data. Research data will be de-identified and stored in locked cabinets in the lab accessible only by authorized research personnel. Electronic data will be de-identified and kept on secure, password protected servers at the Shirley Ryan Ability Lab. Only authorized research staff will be able to access any of the formerly mentioned data. De-identified data will be kept indefinitely. Study documentation will be collected and stored and kept confidential and compliant with HIPAA requirements. Identifying data will be held for 7 years after the study is completed and published.

All personal information (names, addresses, email or phone numbers, etc.) gathered for this study that can identify participants will be kept secure to protect their privacy and will never be shared at any time with any person or entity. Data collected during the study and shared with others will reference participants only by an alphanumeric code. The "master list" linking personal information to the alphanumeric code will not be shared, and will be kept by the study PI in a secure location. All personal information linking participants to their data will be destroyed after 7 years following the completion of the study.

QUALIFICATIONS TO CONDUCT RESEARCH AND RESOURCES AVAILABLE

The Shirley Ryan AbilityLab services the cerebral palsy population and is a research hospital that maintains a research registry (greater than 750 participants). In addition to our flagship hospital, we have outpatient clinics that provide long-term follow-up care to this population. We will recruit participants from our research registry, website and outpatient affiliates and facilities to meet our enrollment goal.

All study team members will be trained on the study protocol and procedures. Experienced physical therapists will lead the assessment and treatment sessions. The study team members are employees of the Shirley Ryan AbilityLab. They are familiar with the study site and are

STU#:00215607

experienced with the study population. There will be medical resources including a resident on call and nursing staff available 24 hours a day if needed in case of an emergency. All our treadmills have overhead harnesses for additional safety during training.

The principal investigator of this study, [name], PT, PhD, is Director of the Max Nader Center for Rehabilitation Technologies and Outcomes (RT&O Lab), within CBM. Adequate dedicated office and treatment space is available for private meetings with potential subjects, performing physical evaluations, explaining the study protocol and obtaining study consent, performing data analysis, and writing manuscripts.

REFERENCES

- [1] S. J. Olney, H. E. MacPhail, D. M. Hedden, and W. F. Boyce, "Work and power in hemiplegic cerebral palsy gait," *Phys. Ther.*, vol. 70, no. 7, pp. 431–438, 1990
- [2] D. L. Damiano, "Activity, activity, activity: Rethinking our physical therapy approach to cerebral palsy," *Phys. Ther.*, vol. 86, no. 11, pp. 1534–1540, 2006.

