- 1.1 We will recruit up to 30 participants meeting the inclusion criteria. Recruitment will occur through Shirley Ryan AbilityLab's flagship hospital and all affiliate sites. We will also recruit from local physicians as well as the Cerebral Palsy Research Registry. Subjects will be divided into two groups: (a) always under therapist supervision and (b) with on therapist-supervised and two parent supervised sessions per week. Once subjects have agreed to participate in the study, they will be consented at the Shirley Ryan AbilityLab. Study staff will explain the study, a written consent form will be signed by the subject if 18 years or old (or by one parent/guardian if subject is under 18 years old). If subject is younger than 18 but older than 12, in addition to parental/guardian consent, the subject will provide verbal and written ascent to participate. Children younger than 12 will provide verbal ascent along with parental/guardian consent. A copy will be given to the subject while the original document will be kept in a secure, locked cabinet.
- 1.2 Following informed consent, subjects will undergo physical evaluation and screening exam by trained research personnel. Study staff must obtain medical clearance from all subjects' physicians prior to baseline testing.
- 1.3 Once they are enrolled, baseline outcome measures will be assessed by a trained research personnel.

2. Procedures during Treatment

- 2.1 After the baseline testing is completed, subjects will begin 12 sessions of training, 3 sessions per week for 4 weeks (missing no more than 3 session's total). Up to an additional 3 training visits and/or 2-3 weeks may occur should the BiOMOTUM RAAD/BiOMOTUM SPARK/other similarly updated BiOMOTUM device require maintenance or updates during the child's participation. Additional visits should only be required if adjustment is needed to ensure safety following changes.

STU#:00215607

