At minimum, 9 training visits can occur over 8 weeks. Training sessions will last up to 1 hour and will include walking training in the BiOMOTUM RAAD/SPARK device, with the device in resistance mode. Participants will be enrolled at GMFCS levels I-III, and randomly selected to complete the intervention in one of two modalities: (a) always under therapist supervision, and (b) with one therapist-supervised and two parent supervised sessions per week. All sessions, including those that are parent-supervised, will take place at Shirley Ryan AbilityLab. During parent-supervised sessions that seek to replicate how a child would train at home, parents will ask their child to walk with resistance to the best of their ability until the time is up. Parents can use toys and snacks to incentivize session completion.

Gait training will include approximately 20-30 minutes of treadmill walking; participants will complete three ~5-10-minute bouts of walking with seated rest periods in between. The research team will guide participants to walk at a moderate-to-high intensity for the duration of each walk as indicated by level 7 ("Hard") on the Pictorial Children's Effort Rating Table (PCERT). To maintain intensity as participants progress through the protocol, the therapist will increase the treadmill speed and/or the resistance level once per week to ensure progression. Plantar-pressure biofeedback will be provided to each participant at least once per session.

- 2.2 For both delivery modes, the therapist will increase the resistance level once per week to ensure progression.
- 2.3 During training and assessment sessions, the BiOMOTUM RAAD/SPARK iPhone will record data from the device's joint angle and Inertial measurement Unit (IMU) sensors regarding the subjects ankle angles and body position.

Outcome Measures:

The following outcome measures will be collected by trained research personnel for all subjects at the following testing points: baseline, 2-7 days post-intervention (after 12 training sessions), and 3 weeks following the final training session.

Clinical Performance Outcome Measures:

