1. **10 Meter Walk Test (10MWT):** The 10MWT assesses walking speed in meters per second over a short duration. Changes in gait speed that result in a transition to a higher category of ambulation classification resulted in better function and quality of life. In the 10MWT, subjects are directed to walk at their self-selected and maximum safe speed with effects of acceleration and deceleration minimized (by adding 1 meter at the beginning and at the end of the course to isolate the subject's steady state speed). Any assistive device and orthotic should be kept consistent and documented. It should also be documented whether the gait is treated at "self-selected walking speed" or "fastest walking speed". Three trials will be completed at the self-selected speed and three trials will be completed at the fast speed. If someone is unable to complete all trials, then the reason will be documented in the CRF.

STU#:00215607

2. 6 Minute Walk Test (6MWT): The 6MWT measures the distance a subject can walk indoors on a flat, hard surface in a period of 6 minutes, using assistive devices, as necessary. Any assistive device and orthotic should be kept consistent and documented. The test is a reliable and valid evaluation of functional exercise capacity and is used as a sub-maximal test of aerobic capacity and endurance. This test will be performed while walking without the device as well as with the BiOMOTUM RAAD/SPARK. It will be administered while wearing a mask to measure oxygen consumption (Cosmed K5B2 Metabolic Unit) when performed without the BiOMOTUM RAAD/SPARK. Electromyography may be used to assess lower-limb muscle activity during gait analysis trials and/or the 6MWT.

3. Timed Up and Go Test (TUG): The TUG assess mobility, balance, walking ability, and falls risk. The participant starts seated in a chair with his/her back against the chair back. On command, the participant rises from the chair, walks 3 meters, turns, walks back to the chair and sits down. Timing begins when the command to start is given and stops when the participant returns to a seated position. This test may be repeated up to 3 times during each assessment visit and during each training visit.

4. Gross Motor Function Measure -66 (GMFM-66): The GMFM-66 measures change in gross motor function over time in children with cerebral palsy. This assessment quantifies motor function, not the quality of the motor performance.

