In Experiment 2, participants will come to Gillette for a baseline visit which will take roughly 120 minutes. Baseline visit will include a complete gait analysis and ABS fitting and acclimation. Additionally, this baseline visit will be used to collect outcome measures as described below.

Following the baseline visit, participants will return to Gillette for 8-12 training visits over 4-8 weeks with *assistance* training, which will take roughly 30-60 minutes each. During each of the training visits, participant will don the RAAD the PT will guide participants through the following activities (breaks will be provided, as needed):

- Three bouts of ~5-10 minutes of overground walking with assistance at moderate-to-high intensity.

After all assistance training visits are complete, participants will complete a follow-up visit at 3 days and 3 weeks post-training visits.

During the baseline and follow-up visits, the PT will guide participants through the following activities and collect the outcome measures listed in sections 3.1 and 3.2:

- Three-dimensional gait analysis, which includes steady-state metabolic cost on a treadmill (if tolerated), 6MWT, gait kinematics and kinetics, markers and surface EMG, and physical examination and medical history – Clinically validated method for collecting and analyzing gait and motion in the Gillette Center for Gait and Motion Analysis
- TUG, which measures the time required to stand up for a standard arm chair, walk 3 meters, turn, walk back to the chair and sit down – Clinic measure of balance and functional mobility
- GMFM-66, which measures gross motor activities across five dimensions such as lying/rolling, sitting, crawling/kneeling, standing, and

MEDICAL PROTOCOL (HRP-590)

PROTOCOL TITLE: Development of a robotic ankle assist device to improve mobility in individuals with movement disorders

VERSION DATE: 11/09/2022

walking/running/jumping – Clinically validated assessment of changes in gross motor function of children with CP (CanChild)

The study team will make every effort to have the same PT conduct all visits for each participant to minimize variability between sessions.

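### The protocol lets the Timed Up and Go be repeated at training visits, so a pre-post TUG gain in the resistance arm cannot be separated from practice of the test

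*Protocol*

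**What the plan says.** The Protocol file holds two protocols: the resistance-training protocol, and the assistance-training protocol (HRP-590).

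In the resistance-training protocol, the opening of Outcome Measures has the outcomes collected for all subjects "at the following testing points: baseline, 2-7 days post-intervention (after 12 training sessions), and 3 weeks following the final training session". Training visits are not on that list. Item 3 of the clinical performance measures (TUG) then adds: "This test may be repeated up to 3 times during each assessment visit and during each training visit". No purpose is given for TUG at training visits. The text does not say whether those trials are done with or without the device, or how up to three trials become one score.

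The number of training visits comes from Procedures Involved, 2.1. The plan is "subjects will begin 12 sessions of training, 3 sessions per week for 4 weeks (missing no more than 3 session's total"), with a floor stated as "At minimum, 9 training visits can occur over 8 weeks". There is also an allowance that "Up to an additional 3 training visits and/or 2-3 weeks may occur" when the device needs maintenance or updates.

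In the assistance-training protocol, section 5.2, Experiment 2, TUG is one of the activities introduced by "During the baseline and follow-up visits, the PT will guide participants through the following activities and collect the outcome measures". No TUG is listed for its training visits.

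The SAP section on resistance training treats the arm as one group of 16 children. It assesses outcomes without the device before training and within a week after it, and uses two-sided paired t-tests at 0.05 where the data are normally distributed. It does not name TUG, which is covered only by the general reference to outcome measures.

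**The concern.** TUG is a listed mobility outcome, and mobility is part of the first research objective. The test consists of rising from a chair, walking 3 m, turning, returning and sitting. The training is described as treadmill walking in the device. TUG trials at training visits would therefore be added exposure to the outcome test itself, between the two measurements that the SAP compares.

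Practice at a timed task would be expected to shorten the time, which is the same direction as a benefit from training. Both delivery modes train with the device, so the arm has no untrained group that would show the practice part. Neither document provides a familiarisation trial before baseline, a cap on total exposure or an adjustment. Because the repeats are optional, exposure can also differ from child to child and between the two randomised delivery modes.

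**Working it through.** **No figure to reproduce.** The documents give no sample size, power or practice effect for TUG in the resistance arm. The sample sizes of 10 and 5 in section 15.2 of the assistance-training protocol belong to other experiments.

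**Step 1: permitted exposure.** Inputs are up to 3 TUG trials per visit (TUG item) and 9, 12 or 15 training visits (Procedures 2.1: 12 − 3 missed = 9; 12 planned; 12 + 3 extra = 15). Training-visit trials = 3 × visits, with a minimum of 0 because the repeats are optional.

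| Training visits | Training-visit TUG trials | Maximum before the post-test, with 3 at baseline |
|---|---|---|
| 9 | 0 to 27 | 27 + 3 = 30 |
| 12 | 0 to 36 | 36 + 3 = 39 |
| 15 | 0 to 45 | 45 + 3 = 48 |

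If TUG were confined to assessment visits, at most the 3 baseline trials would precede the post-test.

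**Step 2: how much practice would matter (illustration only).** Suppose training has no effect and practice shifts the mean by d standard deviations of the change score. With n = 16 and normal changes, the SAP's test statistic follows a noncentral t with 15 degrees of freedom and noncentrality d√16 = 4d. It rejects beyond ±2.131. The chance of p < 0.05 is then:

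| Practice-only gain d (assumed) | Chance of p < 0.05 |
|---|---|
| 0 | 0.05 |
| 0.2 | 0.12 |
| 0.3 | 0.20 |
| 0.5 | 0.47 |
| 0.8 | 0.85 |

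An observed mean gain of 2.131/4 = 0.53 SD is enough for significance.

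**Step 3: the same in per cent.** This needs an SD of change, which the documents do not give for TUG. The nearest figure is the 4-week resistance pilot (n = 6), which reports 11 ± 9% on functional mobility tests that it does not name. If 9% is an SD, t = 11/(9/√6) = 2.99 on 5 degrees of freedom, p = 0.030, against a stated 0.04. That reading is close but not exact. With an SD of 9%, practice-only gains of 2%, 3%, 5% and 7% give rejection probabilities of 0.13, 0.24, 0.55 and 0.83, and the smallest significant mean gain is 0.533 × 9 = 4.8%.

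**Step 4: comparisons between groups.** The permission covers both randomised delivery modes, so practice would largely cancel between them if both repeated the test equally. The protocol does not ensure that. Against the assistance arm, scheduled exposure is unequal: up to 27, 36 or 45 training-visit trials on one side and none scheduled on the other.

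**The case against.** The strongest reply is that the TUG wording is a permission. Nothing in the documents shows that any training-visit TUG was done, or that counts differed between children. A reader might infer that each child rehearsed the test 36 times, or that any reported gain does contain practice. The documents support neither reading, only a range that starts at zero. This stands.

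The size is also unknown. A reader might assume a practice effect of 5 to 10%, set it against the pilot's 11%, and conclude that practice explains about half to nearly all of such a gain. That would divide an assumed number by a figure not identified as TUG, and the documents do not support it. The probabilities in steps 2 and 3 depend on assumed effects in the same way and show sensitivity only.

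TUG is not a primary endpoint of the resistance protocol. Those are safety and self-selected speed on the 10 Meter Walk Test. This too stands and limits the importance of the point.

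On the assistance arm, a reader might infer that it is free of practice. It is not: TUG there is repeated at baseline and follow-up, so ordinary retest familiarity remains, and zero training-visit trials is an inference from silence. The SAP plans no between-arm test, although section 15.3 of the assistance-training protocol mentions a model with delivery mode across assistance and resistance. The arms also already differ in site, device mode and walking surface.

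Finally, an uncontrolled pre-post design cannot attribute any outcome to the device, with or without training-visit TUGs. That is true, but the permission adds an avoidable source of change specific to this test, and nothing in either document removes it.

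**Conclusion.** The point holds as one of interpretation for an outcome that is not primary. Followed as written, the plan allows between 0 and 36 extra TUG trials over 12 training visits (ceilings of 27 over 9 and 45 over 15) before the post-test. With training described as treadmill walking, no untrained control and a pre-post paired test, a TUG gain in the resistance arm cannot be separated from practice of the test. How large the practice part is, and whether there is any, cannot be determined from the documents.

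The comparison of the two randomised delivery modes is protected only if both repeat the test equally, and any TUG comparison with the assistance arm would carry unequal test exposure. The documents do not support the stronger conclusion that TUG must be discarded as efficacy evidence for every child tested during training; disclosure and a caveat are proportionate.

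**What to change.** In the TUG item of the resistance-training protocol, delete the words that extend the repeats to training visits. Set one fixed number of TUG trials for every assessment and one rule for turning them into a score, and state both in the SAP.

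The SAP describes training already completed in 16 children, so new protocol wording cannot change their exposure. For them, report the number of training-visit TUG trials per child and by delivery mode, or state that it was not recorded. Report the scoring rule that was used, and present the TUG change as uncontrolled for practice. Any TUG comparison with the assistance arm should note the unequal test exposure.

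The cost is wording, a short table if the counts exist, and the loss of the optional session-by-session TUG trend. No new data collection is needed.
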